	A descriptive statistical analysis will be performed for the primary safety endpoint, ie, the composite of major and CRNM bleeding events that occur during the Main Treatment Period: from the date of first dose of study drug to the Month 3 Visit, or to the date of last dose of study drug plus 3 days if study treatment is discontinued, whichever is earlier. This analysis will be based on CEC adjudication results.

The time to major or CRNM bleeding occurring during the Main Treatment Period will be compared between treatment groups for subjects in the Safety Analysis Set, using the Cox proportional hazards regression model including treatment group, concomitant usage of aspirin, and underlying disease (Kawasaki disease, Fontan surgery, Heart Failure or Other) as covariates. Hazard ratio between edoxaban and SOC treatment group will be calculated with corresponding 95% confidence interval. The incidence, annualized event rate, and rate difference between edoxaban and SOC treatment groups will also be calculated.

Analysis of Secondary Safety and Efficacy Endpoints:

The incidence, annualized event rate, and rate difference between edoxaban and SOC treatment groups of other secondary safety and efficacy endpoints for the Main Treatment Period will be summarized by treatment group.

The incidence and annualized event rate of other secondary safety and efficacy endpoints for the Extension Period will be summarized for the edoxaban treatment group.

Exploratory Analysis:

Quality of life will be assessed using validated questionnaires.

Intra-patient safety (Investigator-reported bleeding) and efficacy (Investigator-reported TE) during the Main Treatment Period will be compared with the previous 3-month pre-randomization period of anticoagulant regimen.

The incidence and event rate of safety and efficacy endpoint in the Main Treatment Period will be summarized for comparing edoxaban regimen with available existing historical control data based on literature review and search for registered clinical trials with similar endpoints.

A separate sub-analysis of primary prevention and secondary prevention events will be provided if data allow. TE will be classified as primary prevention and secondary prevention events and summarized by treatment group for events occurring during the Main Treatment Period.

Interim Assessment:

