2.1.3. Exploratory Objectives

The exploratory objectives are:

- To assess the quality of life (QOL) using validated questionnaires.
- To compare the intra-patient safety (Investigator reported bleeding) and efficacy (Investigator reported TE) during the Main Treatment Period compared with the prior treatment occurring within 3 months of randomization.
- To compare edoxaban regimen with available existing historical data based on literature review and search for registered clinical trials with similar endpoints.
- To analyze the primary prevention and secondary prevention of TE.

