4. STUDY POPULATION

4.1. Inclusion Criteria

Subjects must satisfy all of the following criteria to be eligible for the study:

1. Children with cardiac diseases who are at risk for thromboembolic complications and require at least 3 months antithrombotic anticoagulant prophylaxis.

Either one of the following criteria may apply:

a. Children with cardiac disease who have a history of cardiac shunt occlusion/thrombosis, with shunt still in place (secondary prevention).

OR

b. Children with cardiac disease who require (including those already taking, and those not yet taking) anticoagulation for primary prevention of TE.

Cardiac conditions known to significantly increase the risk of thrombosis (hence, indications for primary TE prevention) are defined in Antithrombotic Therapy and Prevention of Thrombosis¹. Some examples of cardiac conditions at risk of thrombosis are Fontan surgery, heart failure, Kawasaki disease, and Blalock-Taussig and Glenn surgery.

- 2. Male or female children between 1 and <18 years of age. Children between 38 weeks gestational age and 1 year of age will be included in the study, however, only after the safety and efficacy data of 50 subjects between 1 and <18 years of age in the edoxaban arm have been evaluated at the end of the 3-month treatment period.
- 3. Subject and/or parent(s)/legal guardian(s) or legally acceptable representative is informed and provides signed consent for the child to participate in the study with edoxaban treatment. Pediatric subjects with appropriate intellectual maturity will be required to sign an assent form in addition to the signed informed consent from the parent(s)/legal guardian(s) or any legally acceptable representative.
- 4. Female subjects of childbearing potential must test negative for pregnancy at Randomization and must consent to avoid becoming pregnant by using a locally approved contraception method throughout the study. For locally approved contraceptive methods, see Appendix 17.3.
- 5. If the subject has a history of a TE that meets all of the following criteria:
 - Old, organized and/or resolved per the discretion of the Principal Investigator (confirmation of an old, organized and or resolved TE is not required by any imaging studies), and
 - The subject is asymptomatic, and
 - The subject continues to require at least 3 months of anti-coagulation treatment, and
 - There is no intracardiac thrombus or thrombi on the screening echo, and

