5.2.4.1. To Initiate Edoxaban Treatment at Randomization

For subjects without prior anticoagulant therapy, edoxaban may be started the day of randomization (Day 1).

For subjects who received VKA treatment prior to randomization and are randomized to edoxaban, VKA treatment will be discontinued the day before randomization and edoxaban dose will be initiated when an INR \leq 2.5 is reached. It is per Investigator's discretion based on his/her local practice and on the subject's underlying cardiac disease to consider if heparin bridging is necessary during this period. Heparin bridging will be provided by the Investigator.

If heparin bridging is used, edoxaban will be started as below:

- 1. In case of bridging with a LMWH twice a day regimen, edoxaban dosing will start 12 ± 3 hours after the last LMWH dose
- 2. In case of bridging with a LMWH once a day regimen, edoxaban dosing will start 24 ± 3 hours after the last LMWH
- 3. In case of bridging with a UFH regimen, edoxaban dosing will start 4 ± 1 hour after the last UFH dose

5.2.4.2 Transition SOC-Treated Subjects during the Main Treatment Period to Edoxaban in the Extension Period

For subjects who received VKA treatment edoxaban dosing will be initiated when an INR \leq 2.5 is reached. This may occur as early as next day of the Extension Period.

If the subject was originally randomized to UFH or LMWH, edoxaban will be started as below:

1. In case of LMWH twice a day regimen, edoxaban dosing will start 12 ± 3 hours after the last LMWH dose

- 2. In case of LMWH once a day regimen, edoxaban dosing will start 24 ± 3 hours after the last LMWH
- 3. In case of UFH regimen, edoxaban dosing will start 4 ± 1 hour after the last UFH dose

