5.5. Prior and Concomitant Medications

Medications that the subject has taken within 30 days before screening will be recorded. In addition, anticoagulant and antiplatelet therapy will be recorded up to 3 months prior to randomization.

The following drugs and devices (see Appendix 17.5) CANNOT be used during the entire study treatment period and their unavoidable use would require study drug therapy interruption unless specifically indicated for study drug discontinuation:

- Anticoagulants, other than the assigned study drugs, by any route study drug should be discontinued
- Single or dual antiplatelet therapy with any antiplatelet agent is prohibited except for low dose aspirin defined as 1 to 5 mg/kg/day with maximum of 100 mg/day. If a clinical indication for antiplatelet therapy (other than low dose aspirin) arises after randomization, study drug should be temporarily interrupted and use of any other anticoagulation therapy is permitted at the physician's discretion.
- Chronic use of oral or parenteral non-steroidal anti-inflammatory drugs (NSAIDs) including both cyclooxygenase-1 and cyclooxygenase-2 inhibitors other than aspirin for ≥4 days/week. Use of NSAIDs via other routes (eg, topical, inhaled, intranasal, intraocular, etc) are not restricted (see Appendix 17.5.5).

All P-gp inhibitors (please refer to Appendix 17.6.1 for a list of the most commonly used P-gp inhibitors) excluding amiodarone will require dose reduction of edoxaban.

The Investigator is encouraged to contact a study physician (telephone number will be provided per country, per region; please refer to Study Manual for an appropriate phone number) if further guidance is needed.

Information regarding concomitant medications will be collected with start date, stop date, drug name, dose, and dosing regimen for population PK analyses at Month 1.

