To assess the safety for intra-patient between the Main Treatment Period and previous anticoagulant regimen, bleeding history since diagnosis of underlying disease and within the past 3 months of randomization will be collected. The incidence of bleeding events and annualized event rate in the 3 months prior to randomization and during the Main Treatment Period will be calculated for the subjects who have both pre-randomization and post-randomization data available. This analysis will be based on Investigator reported events.

To compare edoxaban regimen with available existing historical control data for bleeding, a literature review and a search for registered clinical trials with similar endpoints will be conducted. The available results of control data will be extracted and tabulated together with the results of the Main Treatment Period from this study.

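### The intra-patient bleeding comparison with the previous anticoagulant regimen also admits children who had no anticoagulant, so its pooled before/after rates do not answer the stated objective.

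*Combined protocol and SAP*

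**What the plan says.** Section 2.1.3 lists as an exploratory objective an intra-patient comparison of investigator-reported bleeding and TE in the Main Treatment Period, "compared with the prior treatment occurring within 3 months of randomization". The synopsis describes the same analysis as one in which that period is "compared with the previous 3-month pre-randomization period of anticoagulant regimen". Section 11.4.3.1 introduces the bleeding half with "To assess the safety for intra-patient between the Main Treatment Period and previous anticoagulant regimen". It then sets the population as "subjects who have both pre-randomization and post-randomization data available" and asks for incidence and annualised event rate in the 3 months before randomisation and in the Main Treatment Period. Section 11.4.1.2 uses the same population wording for TE.

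On who can be in the trial, inclusion criterion 1b in Section 4.1 covers children needing primary prevention, "including those already taking, and those not yet taking". Section 5.2.4.1 gives a starting instruction for children with no earlier anticoagulant. On what is collected, Section 6.2 lists bleeding history over the past 3 months as a screening item with no condition on prior treatment. Section 5.5 states that "anticoagulant and antiplatelet therapy will be recorded up to 3 months prior to randomization".

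**The concern.** The comparator is named as a previous treatment, but the population rule does not require that there was one. A child who starts anticoagulation at randomisation has a recorded 3-month bleeding history and post-randomisation data, and so qualifies. That child's earlier 3 months are then counted as time on a previous anticoagulant regimen that did not exist. A child who began an anticoagulant part-way through the window contributes some untreated time in the same way.

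The pooled figures therefore mix two contrasts: study treatment versus an earlier anticoagulant, and study treatment versus none. A reader who takes them at face value could read the effect of starting anticoagulation as a property of the study drug. The planned tables would not let the reader undo this. Section 11.3 summarises prior medication for the Safety Analysis Set but does not cross it with bleeding.

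**Working it through.** **1. The plan's own figure.** No figure is stated for the intra-patient comparison. The only bleeding rates in the plan are in Section 11.6: 8.5% on edoxaban and 10.3% on SOC, with 100 and 50 subjects. They reproduce the stated interval with an unpooled Wald formula: difference -1.8%; SE = sqrt(0.085×0.915/100 + 0.103×0.897/50) = 5.12%; 95% CI = -1.8% ± 1.96×5.12% = -11.84% to 8.24%, against the stated -11.8% to 8.2%. I borrow 8.5% below for illustration only. It is a major/CRNM rate from an adult study, whereas the intra-patient analysis uses investigator-reported bleeding events.

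**2. Does the rule admit children with no prior anticoagulant?**
- Eligible: yes (Section 4.1, criterion 1b; foreseen in Section 5.2.4.1).
- Pre-randomisation bleeding data collected: yes (Section 6.2).
- Post-randomisation data collected: yes, as for any subject.
- Excluded by another sentence: none found. No section limits the analysis to prior users, splits it by prior use, or defines what counts as available data.

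**3. Size of the effect.** Let r be the 3-month bleeding risk on any anticoagulant, with study treatment set equal to the prior regimen so that the true ratio is 1. Let p be the share with no anticoagulant in the prior 3 months, and f their bleeding risk in that period divided by r. Both p and f are assumptions.

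Pre = r[1 - p(1-f)]; post = r; expected ratio = 1/[1 - p(1-f)], which does not depend on r.

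| p | f=0 | f=0.25 | f=0.5 | f=1 | f=1.5 |
|---|---|---|---|---|---|
| 20% | 1.25 | 1.18 | 1.11 | 1.00 | 0.91 |
| 25% | 1.33 | 1.23 | 1.14 | 1.00 | 0.89 |
| 30% | 1.43 | 1.29 | 1.18 | 1.00 | 0.87 |
| 50% | 2.00 | 1.60 | 1.33 | 1.00 | 0.80 |

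For example, at r=8.5%, p=25%, f=0.5: pre = 8.5%×(1-0.125) = 7.4% and post = 8.5%, so the ratio is 1/0.875 = 1.14, about one event per 100 children.

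**4. Would it be visible?** Simulating 100 children at r=8.5%, with the two periods as independent binomials (a simplification, since the same children are counted twice):

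| p, f | Post exceeds pre | Post below pre |
|---|---|---|
| p=0 (prior users only) | 45% | 45% |
| p=25%, f=0.5 | 56% | 34% |
| p=50%, f=0.25 | 78% | 15% |

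**5. After restriction to prior users.** p=0, so pre = post = r and the expected ratio is 1.00 whatever f is.

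**The case against.** The strongest reply is that the restriction is already implied. The three descriptions of the comparator all presuppose a prior regimen. A child without one arguably has no relevant pre-randomisation data, and Section 11.7 leaves definitions to a statistical analysis plan whose separate text is not in the reviewed document. This partly stands: the authors may well intend a restriction. But the descriptions state the aim, while the sentence that sets the population is broader, and screening bleeding history exists for treated and untreated children alike. As written, the rule admits them.

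A reader might also infer that study treatment is bound to look as if it raises bleeding. The documents do not support that. The direction requires f<1, and nothing in the plan gives f. The fourth disease stratum can include recent post-surgical children, whose earlier bleeding could be high. Some children without an anticoagulant may be on low-dose aspirin, so their time is not free of antithrombotic treatment. The ratio of 2.00 needs half the children to be new starters with no bleeding at all in 3 months, which is an extreme corner. Even with f<1, chance can hide the effect at this sample size.

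Finally, the analysis is exploratory, unadjudicated and descriptive, with no test or decision rule. That stands and limits the weight of the point.

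**Conclusion.** The point holds in a limited form. The population rule does not match the comparator that the objective names, so the pooled before/after bleeding rates do not answer the objective in Section 2.1.3. This is true whatever the direction of any bias. If bleeding is lower off anticoagulant, the expected post/pre ratio is inflated by 1/[1-p(1-f)]: 1.14 at p=25%, f=0.5, and 1.11 to 2.00 across p=20-50%, f=0-0.5. It is 1.00 at f=1 and falls below 1 for f>1. These sizes rest wholly on assumed p and f.

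A reader might extend this to edoxaban versus SOC. The documents do not support that. The primary analysis is a randomised comparison of CEC-adjudicated events after the first dose, and it uses no pre-randomisation bleeding. Children with no prior anticoagulant can be in either arm. Only the before/after contrast is affected.

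**What to change.** In Section 11.4.3.1, limit the before/after bleeding comparison to subjects with a recorded anticoagulant in the 3 months before randomisation, and state what counts as available data. Report children with no prior anticoagulant in a separate row and do not pool them. Make the same change for TE in Section 11.4.1.2, so that both halves of the objective use one population.

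Where the dates exist, count pre-period events and person-time only while the child was on the earlier anticoagulant. The sponsor should confirm that they do: Section 5.5 names start and stop dates only for concomitant medications, and Section 6.2 asks for bleeding history without specifying dates. Without them, restriction and the separate row are still possible, but part-window starters would keep some untreated time in the comparator.

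The restriction itself needs only wording, since prior anticoagulant use is already recorded (Sections 5.5 and 6.2; Table 17.1). The price is fewer subjects in an exploratory, descriptive comparison.

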11.4.3.2. Analysis of Hepatic Events

The analysis of hepatic events will be based on CEC adjudication results. All CEC adjudication confirmed hepatic events will be summarized for the characteristics of the hepatic events by treatment group for the Main Treatment Period and for the Extension Period.

11.4.3.3. Adverse Event Analyses

Treatment-emergent AEs (TEAEs) are defined as AEs that occur, having been absent before the study treatment administration, or worsen in severity after the initiation of study treatment administration.

Adverse events will be coded according to the Medical Dictionary for Regulatory Activities.

The number and percentage of subjects reporting TEAEs will be calculated overall, by system organ class, by preferred term, and by treatment group for the Main Treatment Period and for the Extension Period. TEAEs will be further summarized by severity and relationship to study drug. Similarly, the number and percentage of subjects reporting treatment-emergent SAEs will be tabulated, as well as TEAEs leading to discontinuation from study treatments and death events.

A by-subject AE (including treatment-emergent) data listing including but not limited to verbatim term, preferred term, system organ class, severity, and relationship to study treatment will be provided. Deaths, other SAEs, and other significant AEs, including those leading to discontinuation from study treatments, will be listed.

11.4.3.4. Clinical Laboratory Evaluation Analyses

Descriptive statistics will be provided for the clinical laboratory results by scheduled time of evaluation and by treatment group for the Safety Analysis Set, as well as for the change from baseline for the parameters which planned to collect both at baseline and post-baseline in the Main Treatment Period. The baseline value is defined as the last non-missing value before the

initial administration of study treatment. In addition, mean change from baseline will be presented by treatment group for the maximum and minimum post-treatment values and the values at the Month 3 Visit.

Similar summaries will also be provided for clinical laboratory results by scheduled time of evaluation during the Extension Period, as well as for the change from Month 3 Visit to the visits after Month 3.

Abnormal clinical laboratory results will be included a by-subject data listing.

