3.2. Discussion of Study Design

This study is designed to compare the safety of edoxaban with SOC in pediatric subjects with cardiac conditions at risk of thromboembolic events. The adjudication of the efficacy and safety endpoints will be conducted by a blinded adjudication committee.

The study includes 2 periods.

• The Main Treatment Period is defined as the time from randomization, until the end of Month 3 of treatment.

Subjects who discontinue treatment from the Main Treatment Period prior to Month 3 will continue to be followed monthly according to the Schedule of Events (Appendix 17.1) through the Month 3 visit (Visit 5), and have a 30-day Follow-Up Visit. If treatment discontinuation occurs prior to Month 2 visit, the 30-day Follow-Up Visit will occur on the same day as the Month 3 visit.

Subjects who complete the Main Treatment Period (Month 3) but do not continue into the Extension Period will have a Month 3 Visit and a Follow-Up Visit, 30 days after last dose of study drug and be discontinued from the study.

Subjects who withdraw from the study prior to Month 3 (meaning the subject can no longer participate in the study due to withdrawal consent), will have a Follow-Up phone call 3 months from the date of randomization to ascertain any events (TE and/or bleeding events) that may have occurred since withdrawal.

• The Extension Period is discretionary for the subject based on the Investigator judgment of risk burden and will include treatment from the end of the Main Treatment Period (Month 3, Visit 5) up through the end of Month 12 (Visit 8).All subjects entering the Extension Period will be given edoxaban for the duration of the Extension Period.

After Month 3, all subjects will be transitioned to edoxaban at the appropriate dose for their age and weight at informed consent.

Subjects who discontinue the treatment and study at any time after Month 3 will have a Discontinuation Visit performed with a subsequent 30-day Follow-Up.

Subjects who complete Extension Period treatment at Month 12 (Visit 8) will have a Follow-Up Visit, 30 days after last dose of study drug (Visit 9).

Subjects who require anticoagulant treatment after discontinuation of the study treatment at any time will be transitioned to a therapy as determined by the Investigator (Appendix 17.7).

About 150 subjects from sites selected globally will be randomized in a 2:1 ratio (edoxaban:SOC, respectively) ratio into this study.

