9.3. Adverse Events of Special Interest

9.3.1. Liver Enzyme Abnormalities/Liver Dysfunction

Liver function is an area of special interest. Critical liver laboratory assessments include ALT, AST, TBL, and ALP. Particular attention will be paid to subjects with ALT and/or AST \geq 3 × ULN and TBL \geq 2 × ULN simultaneously without evidence of cholestasis (ALP \geq 2 × ULN is considered evidence of possible cholestasis) and without alternative etiology for hepatocellular damage.

Liver enzyme abnormalities that lead to study drug interruption/discontinuation as well will be adjudicated in a blinded manner by the CEC. The CEC charter includes a process by which selected cases will be adjudicated by a liver disease specialist.

In cases of liver laboratory abnormalities, it is important to ensure that the nature and the extent of liver injury is identified and study subjects are monitored until the liver laboratory assessments return to normal.

If the subject discontinued study drug due to liver enzyme abnormalities, the subject will have additional evaluations in order to determine the nature and severity of the liver injury. The documents to be sent for adjudication:

- Results of confirmatory tests and diagnostic evaluation
- The hepatic event adjudication worksheets.

If a subject temporarily interrupts (or discontinues) study drug due to confirmed liver enzyme abnormalities or jaundice, the subject will have additional evaluations as described in Section 5.6.3 at the discretion of the Investigator.

Combined elevations of aminotransferases and bilirubin, either serious or non-serious and whether or not causally related, meeting the clinical laboratory criteria of a potential Hy's Law case [ALT or AST \geq 3 × ULN with simultaneous TBL \geq 2 × ULN] should always be reported to the Sponsor using a Serious Adverse Events Reporting form, in addition to reporting it in eCRF, with the Investigator's assessment of seriousness, causality, and a detailed narrative. These events should be reported within 24 hours of Investigator's awareness of the event.

An Independent Data Monitoring Committee (IDMC) may recommend termination of the study. Termination may be made for any of the following reasons:

- Concerns about significantly higher bleeding risk relative to 1 of the study arms,
- Concerns about drug-induced liver injury,
- Any other safety concerns based on benefit/risk evaluation by the IDMC.

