11. STATISTICAL METHODS

11.1. General Statistical Considerations

All efficacy analyses will be based on the modified intention-to-treat (mITT) Analysis Set and will be performed based on the treatment group assigned at randomization.

Safety analysis will be performed using the Safety Analysis Set. Subjects will be analyzed according to actual treatment received.

All analyses for the Extension Period will be based on subjects who participate in the Extension Period and take only edoxaban in the Extension Period, in the specified analysis set, and will be summarized for the edoxaban treatment group. Data listings will be prepared for subjects who are randomized to the SOC arm, participate in the Extension Period, and do not switch to edoxaban right after the Month 3 Visit.

All confidence intervals will be descriptive and will be two-sided 95% confidence interval (CI), unless otherwise specified.

Unless otherwise specified, the baseline value of an efficacy variable for a subject is the last nonmissing measurement before the randomization, and the baseline value of a safety variable is the last non-missing measurement before the first dose of the study drug.

In general, missing data will not be imputed for the purpose of data analysis. No visit windows will be used for analysis.

Continuous variables will be summarized by the number of observations, mean, standard deviation, median, and minimum and maximum values. Categorical variables will be summarized using frequency counts and percentages. Summary statistics will be presented by treatment group.

There is no formal statistical interim analysis planned. However, after the first 50 subjects enrolled in the edoxaban treatment group and 25 subjects enrolled in the SOC treatment group complete the first 3-month treatment period, an interim assessments by IDMC of safety endpoints will be performed to allow for enrollment of subjects <1 year of age into study.

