11.4.3.5. Vital Sign Analyses

Descriptive statistics will be provided for the vital signs measurements by scheduled time of evaluation and by treatment group for the Safety Analysis Set, as well as for the change from baseline in the Main Treatment Period. The baseline value is defined as the last non-missing value before the initial administration of study treatment.

Similar summaries will also be provided for vital signs by scheduled time of evaluation during the Extension Period, as well as for the change from Month 3 Visit to the visits after Month 3.

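### Extension laboratory and vital-sign change is taken from Month 3 in one pooled group, so the mean mixes an on-edoxaban reference with a pre-edoxaban one, and no baseline-to-Extension change is planned for the edoxaban arm

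*Combined protocol and SAP*

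**What the plan says.** Section 11.4.3.4 gives laboratory summaries for the Main Treatment Period by visit and treatment group, with change from the last value before study treatment began. For the Extension it promises similar summaries by visit, "as well as for the change from Month 3 Visit to the visits after Month 3". Section 11.4.3.5 follows the same pattern: "Similar summaries will also be provided for vital signs by scheduled time of evaluation during the Extension Period", again with change from Month 3.

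Section 11.1 sets the grouping. Extension analyses cover participants who "take only edoxaban in the Extension Period, in the specified analysis set, and will be summarized for the edoxaban treatment group". SOC subjects who do not move to edoxaban straight after Month 3 are only listed: "Data listings will be prepared for subjects who are randomized to the SOC arm, participate in the Extension Period, and do not switch to edoxaban".

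The same section says that "the baseline value of a safety variable is the last non-missing measurement before the first dose of the study drug". Section 5.2.1 counts both edoxaban and the SOC anticoagulants as study drug, so for the SOC arm this general baseline precedes SOC, not edoxaban. No reference tied to the first edoxaban dose is defined.

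On treatment, Section 3.2 states: "All subjects entering the Extension Period will be given edoxaban for the duration of the Extension Period". Sections 5.2.1.2 and 5.2.4.2 end SOC at Month 3, with edoxaban starting afterwards.

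**The concern.** The same visit plays two roles. In a child randomised to edoxaban, any shift that the drug produced in the first 3 months is already in the Month 3 value and drops out of the later change. In a child who switches from SOC, Month 3 is normally the last value before edoxaban, so the later change contains whatever moving to edoxaban does. One mean over both groups estimates neither quantity, and its value depends on how many children from each arm enter a discretionary Extension.

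The plan also leaves a gap. The original edoxaban arm is the only group that can reach 12 months of exposure, yet its change from the pre-treatment value to the Extension visits is not among the stated summaries.

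What is at stake is how the Extension table is read. Section 9.3.1 notes: "Liver function is an area of special interest". Liver tests and hematology are scheduled in the Extension only at the Month 12/Discontinuation Visit (Sections 6.5.3, 9.8.1 and 9.8.3). A near-zero mean change there could be taken as evidence of no shift, when it may partly reflect the choice of reference.

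**Working it through.** **The plan's own figure.** The documents give no figure for Extension change. The one computed figure that uses the same 100:50 split is the confidence interval in Section 11.6. With rates of 8.5% and 10.3%:

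- SE = √(0.085 × 0.915/100 + 0.103 × 0.897/50) = 0.0512
- −0.018 ± 1.96 × 0.0512 = −11.8% to 8.2%, as stated.

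This confirms the planned split and nothing more.

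**What each group contributes.**

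| Group | Status at Month 3 | Change from Month 3 measures |
|---|---|---|
| Randomised to edoxaban | About 3 months on edoxaban | Further change on continued edoxaban |
| SOC switcher | End of SOC, before edoxaban | Change on moving from SOC to edoxaban |

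**Illustration.** Let D be the switchers' mean change (edoxaban versus SOC). Suppose the effect is complete by Month 3 in the edoxaban arm and then constant, so that this arm's later change is 0. With n_E = 100 × q_E and n_S = 50 × q_S entering the Extension:

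pooled change = D × n_S / (n_E + n_S)

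The documents give no uptake by arm, so q_E and q_S are assumptions.

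| q_E | q_S | n_E | n_S | Pooled change |
|---|---|---|---|---|
| 1.0 | 1.0 | 100 | 50 | 50/150 = 0.33 D |
| 0.8 | 0.5 | 80 | 25 | 25/105 = 0.24 D |
| 0.8 | 0.3 | 80 | 15 | 15/95 = 0.16 D |
| 0.5 | 0.8 | 50 | 40 | 40/90 = 0.44 D |

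Any equal uptake gives 0.33 D, because the common rate cancels.

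**If the effect is only partly present by Month 3.** Let a fraction f have been reached in the edoxaban arm, with equal uptake and, for simplicity, the same total effect D in both arms:

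pooled change = D × [100 × (1 − f) + 50] / 150

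- f = 0.5: 100/150 = 0.67 D
- f = 0.75: 75/150 = 0.50 D
- f = 1: 50/150 = 0.33 D

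**Can the missing change be rebuilt from other tables?** Not in general. The Main Treatment Period table covers the whole Safety Analysis Set. The Extension table covers those who continue, mixed with switchers. Mean changes from two different sets of children cannot be added to give baseline to Month 12.

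**Are the data there?** Yes. Liver tests, creatinine, hematology and vital signs are all taken at Screening (Section 6.2 and Table 17.1).

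**The case against.** The strongest reply is that an effect reached by Month 3 is already on display. The Main Treatment Period tables show change from baseline by randomised arm, beside a concurrent SOC group, and for laboratory tests they add the maximum and minimum post-treatment values. Extension values, not only changes, are also summarised by visit. Change from Month 3 answers a legitimate question of its own: what happens after that point. All of this stands, and it limits the consequence. It does not make the pooled mean interpretable, nor does it supply the missing change for the edoxaban arm.

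A reader might infer that the plan could conceal a liver signal. The documents do not support that. Potential Hy's Law cases are reported within 24 hours (Sections 9.3.1 and 9.5), adjudicated hepatic events are summarised for the Extension (Section 11.4.3.2), abnormal laboratory results are listed by subject (Section 11.4.3.4), and the data monitoring committee sees liver enzyme and bilirubin abnormalities (Section 15.9). None of these uses a Month 3 reference.

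It is also fair to say that D is not a pure edoxaban effect. Switchers come off SOC, and inclusion criterion 1b admits children both with and without earlier anticoagulation, so baselines in the edoxaban arm are mixed too. The Extension has no comparator. No choice of reference would isolate a drug effect at 12 months. This argues for separate columns by arm rather than for pooling.

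Finally, Section 11.7 leaves definitions to an SAP to be finalised before database lock, and no separate SAP text is among the documents. The words promising similar summaries could be read as carrying over the split by treatment group, although Section 11.1 points to one pooled group. Even with a split, the edoxaban-arm column would still start at Month 3.

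**Conclusion.** The point holds as a defect of a descriptive table. As written, the pooled Extension change mixes two quantities, and change from the pre-treatment baseline to the Extension visits is not a stated summary for the edoxaban arm.

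The size is illustrative. One third of the switchers' change requires an effect complete by Month 3 and then sustained, equal uptake at 2:1, and pooling as in Section 11.1. A reader might infer that every sustained effect is diluted three-fold. That goes too far, because uptake is unknown and the onset of any effect is unspecified.

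The Main Treatment Period comparison, Extension values by visit and the hepatic safety reporting are unaffected. No clinical management rule is involved. The change is inexpensive and worth making.

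**What to change.** In Sections 11.4.3.4 and 11.4.3.5, and in the SAP before database lock:

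- Present Extension change separately by originally randomised arm.
- For the edoxaban arm, add change from the pre-first-dose baseline to each Extension visit at which the measurement is scheduled. For liver tests and hematology that is Month 12/Discontinuation only; creatinine and vital signs also have Months 6 and 9.
- For SOC switchers, use the last value before the first edoxaban dose, normally Month 3, and label the change as following a switch from SOC.
- Keep change from Month 3 as a supplementary column for the edoxaban arm.

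The cost is revised wording and a few more columns. The SOC-switcher column will be less precise, since it rests on at most about 50 children. No new visits or samples are needed.
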